### **Selection of Subjects**

• List inclusion/exclusion criteria and how subjects will be identified.

We propose to enroll up to 1600 smokers in order to identify 130 participants who meet all criteria to be accepted into the study and to be randomized into one of four experimental conditions.

### Inclusion Criteria

- Are 21-65 years old;
- Smoke an average of at least 10 cigarettes per day;
- Have smoked for the past year;
- Have an expired air CO reading of at least 10ppm;
- Have a self-reported body weight of < 350 lbs.;

- Are able to read and understand English.

Potential subjects of child bearing potential must agree to use two forms of contraception during their participation in this study. Women are considered past the age of child-bearing potential if:

• They are greater than 55 years of age;

• They are at least 50 years of age AND have not menstruated for at least 12 months, OR have a documented Follicle Stimulating Hormone (FSH) level of greater than 40 mIU/mL;

• They are at least 45 years of age AND have not menstruated for at least 18 months, OR have a documented Follicle Stimulating Hormone (FSH) level of greater than 40 mIU/mL.

Medically acceptable contraceptives include: (1) surgical sterilization (such as a tubal ligation or hysterectomy), (2) approved hormonal contraceptives (such as birth control pills, patches, implants or injections), (3) barrier methods (such as a condom or diaphragm) used with a spermicide, or (4) an intrauterine device (IUD). Contraceptive measures such as Plan B (TM), sold for emergency use after unprotected sex, are not acceptable methods for routine use.

Potential subjects must agree to avoid the following during their participation in this study:

• Participation in any other nicotine-related treatment study protocol outside of this protocol;

- Use of tobacco products other than cigarettes, including pipe tobacco, cigars, e-cigarettes (other than those provided during the study), snuff, and chewing tobacco;
- Use of experimental (investigational) drugs or devices;
- Use of illegal drugs;
- Use of exclusionary medications.

### Exclusion Criteria

- Actively seeking treatment for nicotine dependence;
- Uncontrolled high blood pressure (self-report);
- Coronary heart disease with symptoms (e.g., chest pain);
- Heart attack in the past year;
- Cardiac rhythm disorder (irregular heart rhythm with symptoms);
- Chest pain in the last month (unless history indicates a non-cardiac source);
- Symptomatic heart disorder such as heart failure;
- Advanced liver or kidney disease that requires medication or dialysis, paracentesis;
- Bleeding stomach ulcers in the past 30 days;
- Lung disease that requires oxygen;
- Major brain disorder (including stroke with residual deficit, brain tumor, and seizure disorder);
- Migraine headaches that occur more frequently than once per week;
- Recent, unexplained fainting spells;
- Diabetes with insulin use;

• Current cancer or treatment for cancer in the past six months (except basal or squamous cell skin cancer);

- Other major medical condition (as determined by study medical provider);
- Diagnosis of thought disorder; such as bipolar disorder or schizophrenia;
- Psychiatric hospitalization within the past 12 months;
- Pregnant or nursing mothers;

• Use (within the past 7 days) of illegal drugs (or if the urine drug screen is positive for THC, Cocaine, Amphetamine, Opiates, Methamphetamines, PCP, Benzodiazepines, or Barbiturates), unless recent use of prescription opiates or benzodiazepines were taken for management of acute symptoms (e.g., tooth extraction, recent surgery, or sleep);

• Use of experimental (investigational) drugs within the past 7 days;

• Use of psychiatric medications including antidepressants and anti-psychotics may be permitted if the condition is stable (study medical provider discretion).

• Use of opiates, benzodiazepines, and muscle relaxants (unless taken for sleep or acute symptoms such as tooth extraction or recent surgery) within the past 7 days (study medical provider discretion);

• Use of Wellbutrin, bupropion, Zyban, Chantix, varenicline, nicotine patch, nicotine replacement therapy, clonidine or any other smoking cessation aid within the past 30 days;

• Use of cigars, cigarillos, pipes, Hookah, dissolvable nicotine, snuff, chewing tobacco, or e-cigarettes within the past 7 days;

• Diagnosis of alcohol abuse or dependence or self-report of consuming more than 6 drinks on one occasion more than one day per week;

Significant adverse reaction to nicotine patch in the past;

• Current or recent participation (in the past 30 days) in another smoking treatment study at our Center or another research facility;

### Assessment of Eligibility

Potential subjects who do not have a self-reported diagnosis of the above listed conditions may be excluded if the study physician or physician assistant determines that the history reveals information that may jeopardize the subjects' safe study participation. For medical conditions that do not appear above, the study physician will be consulted, and if the medical condition does not jeopardize safe study participation, then the subject may be enrolled.

### **Subject Recruitment and Compensation**

• Describe recruitment procedures, including who will introduce the study to potential subjects. Describe how you will ensure that subject selection is equitable and all relevant demographic groups have access to study participation (per 45 CFR 46.111(a) (3)). Include information about approximately how many DUHS subjects will be recruited. If subjects are to be compensated, provide specific prorated amounts to be provided for expenses such as travel and/or lost wages, and/or for inducement to participate.

### Subject Recruitment

Smokers with no major health problems will be recruited from communities in and around Durham, North Carolina, and, for remote participation, across the state of North Carolina. Recruitment will occur through television, newspaper and internet advertisements, flyers, Facebook, Duke List, and by word-of-mouth. We will also recruit via the Duke Primary Care Research Consortium. This consortium oversees all

research within Duke Primary Care, a network of over 30 clinics primarily around the Research Triangle Area. The consortium is primarily interested in whether studies offered to patients would provide safe and effective means for supporting or improving health outcomes. Duke Primary Care clinics serve a broad cross section of the community. Patients from the Duke Primary Care Research Consortium will be recruited from 1 of the 30 clinics. A study team member will conduct a query into the electronic health record through DEDUCE (Duke Enterprise Data Unified Content Explorer) to identify potentially eligible patients. DEDUCE is an electronic technology system designed to enable access to specific patient data fields across the Duke Health System for approved research purposes. After identifying individuals who fall within our recruitment categories, we will directly contact these patients by MyChart message and/or telephone to offer them additional information about the research studies will not be contacted for this study.

Potential subjects will be pre-screened on the phone by a member of the Duke CSC. If potential subjects meet the pre-screening study requirements and are still interested in participation, they will attend a physical screening session at the Duke CSC, located at [name], or complete screening procedures online and by visiting a local LabCorp facility. If after the screening process it is determined that they qualify for participation, participants will attend subsequent study visits at the Duke Center for Smoking Cessation located at [name], or online via REDCap and phone contact.

### Subject Compensation

Local (in-person) participants will be paid \$25 for completing the Screening procedures. Subjects will be reimbursed \$25 per visit for completing the five study visits, plus \$60 for completing the follow-up visit. In addition, subjects will receive a payment of \$10 for each of the 5 visits attended in which they return their completed take-home diaries with questions in which they record smoking behavior and patch and e-cigarette use, as well as their used and unused e-cigarettes and patches. Subjects who do not complete each visit will still receive payment for the ones completed. Thus, subjects who complete the screening and five visits and hand in their completed take-home diaries and study investigational product (IP) each time and also attend the follow-up visit will receive a total payment of \$335.

Remote participants will be paid \$35 for completing the Screening procedures (\$10 for completing online surveys and CO readings, and \$25 for visiting a LabCorp facility and providing a urine sample). Subjects will be reimbursed \$25 per milestone for completing the five study e-visits, with an additional \$15 for e-visit 1 and an additional \$5 for e-visit 5. Those milestones involve collecting and sending urine and saliva samples. In addition, participants will receive \$30 for completing the follow-up e-visit. In addition, subjects will receive a payment of \$5 at the time of milestones 1-5 for completing 75% of the daily diary entries. Subjects will also receive \$50 for returning the CO monitor after screening and an additional \$50 for returning the CO monitor at the end of the study. Thus, subjects who complete the screening and five e-visits and complete 75% of the daily diaries and also complete the follow-up e-visit will receive a total payment of \$335.

### **Consent Process**

• Complete the consent section in the iRIS Submission Form.

Subject's Capacity to Give Legally Effective Consent

• If subjects who do not have the capacity to give legally effective consent are included, describe how diminished capacity will be assessed. Will a periodic reassessment occur? If so, when? Will the subject be consented if the decisional capacity improves?

We will not include subjects who do not have the capacity to give legally effective consent.

• If not already presented in #4 above, describe study-related treatment or use of an investigational drug or biologic (with dosages), or device, or use of another form of intervention (i.e., either physical procedures or manipulation of the subject or the subject's environment) for research purposes.

### **Risk/Benefit Assessment**

Include a thorough description of how risks and discomforts will be minimized (per 45 CFR 46.111(a) (1 and 2)). Consider physical, psychological, legal, economic and social risks as applicable. If vulnerable populations are to be included (such as children, pregnant women, prisoners or cognitively impaired adults), what special precautions will be used to minimize risks to these subjects? Also identify what available alternatives the person has if he/she chooses not to participate in the study. Describe the possible benefits to the subject. What is the importance of the knowledge expected to result from the research?

*Conventional (combustible) cigarettes:* Continuing to smoke carries significant health risks. Subjects enrolling in this study are not being asked to quit smoking over the course of the study, but will be exposed to no additional risk from their usual smoking behavior. Their exposure to harmfully and potentially harmful constituents in combustible cigarettes may decrease to the extent they use e-cigarettes as an alternative to combustible cigarettes.

Potential side effects of Nicotine patch: The nicotine patch poses very little risk and is approved for overthe-counter sales as a smoking cessation treatment. It is not being used as a treatment for nicotine dependence in this protocol but the risks will be minimal. Insomnia and abnormal dreams are common and expected side effects associated with 24-hour nicotine patches. If a subject complains of disturbed sleep, he or she will be instructed to remove the patch at bedtime and apply a new one the next day at the usual time. Skin irritation may occur, although this will be minimized by changing the site of patch application daily. If a subject develops itching or a rash at the patch site, he or she will be advised to use 1% hydrocortisone cream on the affected area. Symptoms associated with nicotine toxicity include lightheadedness, dizziness, nausea, fainting and vomiting. A less likely side effect of nicotine patches is somnambulism. If a subject reports significant side effects, the dose of the nicotine patch may be reduced if necessary.

*Electronic Nicotine Delivery Systems (ENDS):* ENDS, or "e-cigarettes," have been marketed in the U.S. since 2007 and have been used worldwide by millions of smokers. While the potential risks of long-term use of e-cigarettes are unknown, most experts agree that the constituents of e-cigarettes are less harmful than those of combustible cigarettes (Grana et al., 2014). Although it is conceivable that participants could receive an overdose of nicotine, this is extremely unlikely inasmuch as smokers can control the dose according to how they puff and inhale from the devices, as they do with conventional cigarettes. The main side effect that is anticipated with the relatively short 8-week duration of exposure to ENDS in the proposed project is mild irritation of the respiratory tract from inhalation of the propylene glycol and nicotine contained in the product. Should any clinically significant changes occur, the study physician will recommend discontinuation of ENDS use if it is indicated.

The Centers for Disease Control and Prevention (CDC), the U.S. Food and Drug Administration (FDA), state and local health departments are investigating a respiratory syndrome associated with the use of ecigarettes. People with this syndrome have reported a wide variety of symptoms including cough, shortness of breath, chest pain, nausea, vomiting, diarrhea, fatigue, fever, and abdominal pain.

In a New England Journal of Medicine article entitled "Vaping-Induced Lung Injury" (September 6, 2019), [name] stated that "[a]bout 80% of the persons who vaped and became ill reported having used both nicotine products and tetrahydrocannabinol (THC) or cannabidiol (CBD) products". Thus far, investigators have not found a single product linked to all reports of this respiratory syndrome. Most cases have been linked to "street" products or substances added to e-cigarettes -- changes not intended by ecigarette manufacturers. The e-cigarettes used in this study will be obtained directly from JUUL, a manufacturer registered with the FDA, and will not be altered in any way. Overall, the respiratory syndrome associated with e-cigarette use has been reported in less than 1 in 1,000 people who use ecigarettes.

Subjects will be monitored throughout the duration of the study for side effects and severe adverse effects (SAEs). They will be instructed to report any side effects to the study technicians, who will communicate these reports immediately to the medical staff. The most appropriate course of action will be determined,

which may include options for dose reduction or termination of study intervention. Participants will be reminded that they have the option to withdraw from the study at any time. Subjects will also be given the 24-hour emergency contact numbers in the event that side effects or adverse events occur between sessions. SAEs will be reported to the IRB and will be monitored until resolution or stabilization.

The sponsor for this study will ensure the investigational tobacco product is distributed only to qualified members of key personnel in accordance with this protocol.

### **Costs to the Subject**

• Describe and justify any costs that the subject will incur as a result of participation; ordinarily, subjects should not be expected to pay for research without receiving direct benefit.

There are no costs to participants for taking part in this study. All the study costs, including any study supplies and procedures related directly to the study, will be paid for by the research grant awarded to Duke University.

### **Data Analysis & Statistical Considerations**

 Describe endpoints and power calculations. Provide a detailed description of how study data will be analyzed, including statistical methods used, and how ineligible subjects will be handled and which subjects will be included for analysis. Include planned sample size justification. Provide estimated time to target accrual and accrual rate. Describe interim analysis including plans to stop accrual during monitoring. Phase I studies, include dose escalation schema and criteria for dose escalation with definition of MTD and DLT.

The primary outcome measures will be the amount of combustible cigarette use and e-cigarette use in the last week of the 8-week exposure period. The main index of combustible cigarette use will be expired air CO, a highly sensitive and specific measure of smoke inhalation. As a secondary measure (at the first (V1) and final (V5) sessions), we will assess total urinary 4-(methylnitrosamino)-1-(3-pyridyl)-1-butanol (NNAL), a metabolite of the tobacco-specific carcinogen 4-(methylnitrosamino)-1-(3-pyridyl)-1-butanone (NNK). The half-life of NNAL is 10 days (Goniewicz et al., 2009), yielding a valuable index of sustained reductions in cigarette smoking. The half-life of expired air CO, in contrast, is 4.5 h (Sandberg et al., 2011).

Self-reported cigarettes/day recorded on diaries will also be a secondary index of cigarette consumption. The main index of e-cigarette use will be the number of cartridges consumed, based on selfreport and counts of the number of unused e-cigarette tanks returned. We hypothesize that e-cigarette use will be higher, and concomitantly, combustible cigarette use will be lower, in the nicotine e-cigarette condition compared to the zero-nicotine e-cigarette condition (i.e., comparing Group 1 vs. Group 2). This hypotheses will be evaluated using General Linear Modeling (GLM) techniques to assess the significance of the nicotine factor, using a 1-tailed alpha=0.05. A one-tailed comparison is justified given that a higher dose of nicotine in the e-cigarette would only be expected to decrease use of conventional cigarettes. Moreover, there would be no interest in pursuing the nicotine e-cigarette plus nicotine patch combination if it led to greater smoking than the placebo e-cigarette plus nicotine patch. Thus, the 5% Type I error rate can reasonably be assigned to the 1-tailed comparison. Covariates in the analysis of combustible cigarette use will include the amount of e-cigarette use, since that will affect the overall dose of nicotine received by subjects, as well as baseline combustible cigarette use, and baseline demographic and smoking history variables (the latter will also serve as covariates in the analysis of e-cigarette use as a dependent measure). We predict at least a moderate effect size (0.5) for each of the main effects, nicotine and route of administration, so that a sample size of 50 per group will yield at least 80% power to detect the hypothesized effects.

• Summarize safety concerns, and describe the methods to monitor research subjects and their data to ensure their safety, including who will monitor the data, and the frequency of such monitoring. If a data monitoring committee will be used, describe its operation, including stopping rules and frequency of review, and if it is independent of the sponsor (per 45 CFR 46.111(a) (6)).

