### Sessions

The first study visit (V1) will take place approximately one week after the screening visit. Subjects will complete baseline questionnaires and will be randomized to one of the two groups. Subjects will be tested for exhaled air carbon monoxide, and saliva samples will be collected for analysis of smoking related chemicals (e.g., cotinine). Subjects will also complete questionnaires assessing their dependence on cigarettes (Fagerström Test for Nicotine Dependence (FTND) (Heatherton et al., 1991)), and rewarding effects of cigarettes (modified Cigarette Evaluation Questionnaire (Cappelleri et al., 2007)).

Subsequent study visits will occur approximately two weeks apart (with a five-day window on either side of the scheduled visit). If a participant does not attend a visit and it cannot be rescheduled within the allowable window, the visit will be considered a missed visit; if participants miss two consecutive visits they will be withdrawn from the study. Participants will be tested for exhaled air carbon monoxide, and will also complete questionnaires assessing their dependence on cigarettes (Fagerström Test for Nicotine Dependence (FTND) (Heatherton et al., 1991)), and rewarding effects of cigarettes (modified Cigarette Evaluation Questionnaire (Cappelleri et al., 2007)).

Questionnaires will be completed within REDCap on a desktop computer in the Center office. The technician will log on to the REDCap site and will open the questionnaires for the subjects. Subjects will only have access to their questionnaires. Access to any other websites will be blocked by Duke Psychiatry Information Technology.

At the first (V1) and final (V5) sessions, participants will provide saliva and urine samples. The saliva sample will be used for analysis of smoking related chemicals (e.g., cotinine). The urine sample will be used to assess total urinary 4-(methylnitrosamino)-1-(3-pyridyl)-1-butanol (NNAL), a metabolite of the tobacco-specific carcinogen 4-(methylnitrosamino)-1-(3-pyridyl)-1-butanone (NNK). The half-life of NNAL is 10 days (Goniewicz et al., 2009), yielding a valuable index of sustained reductions in cigarette smoking. The half-life of expired air CO, in contrast, is 4.5 h (Sandberg et al., 2011). Total urinary nicotine equivalents (a measure of total nicotine intake) will also be assessed.

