Subjects will also be given diaries to record the number of cigarettes smoked each day and e-cigarette cartridges used, and will be instructed to return the diaries at the next visit. At Sessions V1-V4, participants will be dispensed a sufficient supply of skin patches and e-cigarette refill tanks (pods) to last until the next session. Participants will be given pods with both flavors (Virginia tobacco and cool mint or menthol) of e-liquid. They will be asked to return all used and unused pods and used patches at their subsequent visit for proper disposal and compliance monitoring.

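### The primary e-cigarette outcome is last-week use, but the returned-pod count covers a variable interval of about two weeks in person, no rule turns it into a last-week or daily figure, and remote participants have no stated cartridge source

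*Combined protocol and SAP*

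**What the plan says.** Data Analysis & Statistical Considerations sets as primary outcomes the "amount of combustible cigarette use and e-cigarette use in the last week of the 8-week exposure period". The Research Abstract says the same. The main index of e-cigarette use is the "number of cartridges consumed, based on selfreport and counts of the number of unused e-cigarette tanks returned"; no period is attached to it.

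For in-person participants, the Sessions section gives the supply cycle: "At Sessions V1-V4, participants will be dispensed a sufficient supply of skin patches and e-cigarette refill tanks (pods) to last until the next session". It then adds: "They will be asked to return all used and unused pods and used patches at their subsequent visit". On timing it says: "Subsequent study visits will occur approximately two weeks apart (with a five-day window on either side of the scheduled visit". One missed visit is tolerated, because withdrawal follows only after two: "if participants miss two consecutive visits they will be withdrawn from the study". In-person diaries cover cigarettes by day and also cartridges used, but the text does not make clear that cartridges are entered by day.

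Remote Study Participation differs. Supplies go out in two shipments, the first meant to cover four weeks and the second to last to the end of the study. The diary asks for occasions of e-cigarette use (at least one puff), not cartridges. No return or count of pods is described. Milestones are two weeks apart, and the five-day window is not stated for them.

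Background & Significance says that a nicotine dose in mg per day, estimated from cartridges consumed, will be a covariate. It gives no denominator and does not apply the rate to the outcome.

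**The concern.** The outcome refers to seven days. The objective half of its index is a single total per dispensing interval, twice that length on schedule and different for each participant. A count over one to three weeks cannot be split afterwards to recover the last one. The other half, the diary, might supply the last week, but the plan does not secure daily cartridge entries or say which source prevails when the two cover different periods.

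Two things are at stake. First, the primary variable is open: a raw count, a count per day and a last-week diary total all fit the text, and the choice could be made after the data are seen. The same quantity is a covariate in the analysis of combustible cigarette use. Second, a raw count mixes rate of use with length of interval, which adds variance unrelated to treatment.

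**Working it through.** **Plan's own figure.** Inputs from Data Analysis & Statistical Considerations: standardised effect 0.5, one-sided alpha 0.05, 50 per group. Normal approximation: Φ(0.5 × √(50/2) − 1.645) = Φ(0.855) = 0.804. The exact t-test gives 0.799. The stated 80% reproduces. At the 65 per group to be randomised (Design Overview), the exact t-test gives 0.883.

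**Length of the last in-person count interval.**
- On schedule: V5 − V4 = 56 − 42 = 14 days, so the last week is 7/14 = 50% of it.
- Window measured from the previous visit: 14 ± 5 = 9 to 19 days. The last week is 7/19 = 37% to 7/9 = 78% of the interval.
- Both visits floating around a fixed schedule: (56 ± 5) − (42 ± 5) = 4 to 24 days. At the short end the interval does not even cover a week.
- V4 missed, V5 attended: 56 − 28 = 28 days nominally, or 18 to 38 if V3 and V5 both float.

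**Illustrative cost of an undivided count.** Let the count be rate × interval, independent, with between-person CV of the daily rate c and CV of the interval k. Then CV² of the count = c² + k² + c²k². Relative to the rate alone, the variance ratio is 1 + k²/c² + k², and the effect size becomes 0.5/√ratio. Assumptions not in the documents: c = 0.6 to 1.0, visit timing uniform within the window, counts not divided by days, and the 0.5 applying to the daily rate. Power is from the exact one-sided t-test.

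| Interval | SD (days) | k² | Variance ratio (c = 0.6; 1.0) | Effect size | Power, 50/group | Power, 65/group |
|---|---|---|---|---|---|---|
| No timing noise | 0 | 0 | 1 | 0.50 | 80% | 88% |
| 9-19 days | √(10²/12) = 2.89 | 0.0425 | 1.16; 1.09 | 0.46-0.48 | 75-77% | 84-86% |
| 4-24 days | √(2 × 10²/12) = 4.08 | 0.0850 | 1.32; 1.17 | 0.43-0.46 | 70-74% | 79-84% |
| Both visits within ±2 days | √(2 × 4²/12) = 1.63 | 0.0136 | 1.05; 1.03 | 0.49 | 78-79% | 87-88% |

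The 65-per-group column assumes full retention; the documents give no dropout rate. Dividing each count by its actual days removes this source of noise.

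**Level shift if use is falling.** With a weekly decline of 10% or 20% (assumed), the mean of weeks 7 and 8 over week 8 is (1/0.9 + 1)/2 = 1.06 or (1/0.8 + 1)/2 = 1.13. This is a shift in level within one arm. It says nothing about the contrast unless the decline differs between arms.

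**The case against.** The index is not the count alone. It also rests on self-report, in-person diaries record cartridges used, and Subject Compensation confirms that diaries cover e-cigarette use. If cartridges are entered by day, the diary isolates the last week and the count checks it over the interval. This stands, and it means that last-week use in person may well be recoverable. What remains is that daily entry is not stated and no rule links the two sources.

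The mg-per-day covariate shows that the investigators already had a daily rate in mind. This also stands in part. It makes analysis of raw counts less likely, but it names no denominator and does not concern the outcome.

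The power figures are fragile. They rest on assumed CVs, uniform timing and an undivided count that no section prescribes. The planned 0.5 is given without an SD, so it may already allow for measurement noise. The 4 to 24 day range is only the widest reading. All of this is fair, and the figures should be read as illustration.

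A reader might infer that use fades faster with the zero-nicotine product, so that a two-week count overstates last-week use in that arm and shrinks the contrast. The documents give no trajectory of use in either arm, and nothing suggests that visit timing differs by arm in this blinded trial.

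**Conclusion.** The point holds as a mismatch between a primary outcome and its index. In person, the returned-pod count covers the whole interval since the last dispensing visit and cannot by itself give last-week use. There is no per-day rule for this outcome and no rule for combining count and diary. For remote participants the cartridge index has no stated source.

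The loss of precision is conditional. Under the assumptions above, an undivided count costs about 3 to 10 points of power at 50 per group, and 1 to 2 points if visits keep within 2 days of schedule. At 65 per group with full retention, power stays at 79% or more. No between-arm bias is shown. Nor do the documents support the stronger reading that last-week use cannot be obtained at all, because the in-person diary may supply it. The point should be settled before analysis, mainly because the primary variable is otherwise open to choice.

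**What to change.** In the Research Abstract and in Data Analysis & Statistical Considerations:

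- Define the count-based index as pods consumed divided by actual days since the last dispensing visit attended (V4, or V3 if V4 was missed), and state that this is the period it covers.
- Name the diary total for the last 7 days before V5 as the last-week measure.

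In Sessions, state that the diary records cartridges by day. In Remote Study Participation, have participants enter cartridges used per day in the same diary, beside occasions of use. The last-week measure then exists for both kinds of participant, and the count-based rate stands next to it for those who return pods.

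Cost: a few sentences, one division and one more diary entry. In-person pods are already to be returned and a visit log is already kept. The trade-off is that the count-based measure describes about two weeks rather than one, and for remote participants the index rests on self-report alone.

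### Two primary outcomes are each tested at one-tailed 0.05 with no rule for combining them, so the error rate and power of the trial's overall conclusion are undefined

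*Combined protocol and SAP*

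**What the plan says.** All of this is in the combined protocol and SAP, mainly under *Data Analysis & Statistical Considerations*.

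- Outcomes: "The primary outcome measures will be the amount of combustible cigarette use and e-cigarette use in the last week of the 8-week exposure period". Expired CO is the main index of the first, and the number of cartridges consumed is that of the second. The *Research Abstract* says the same.
- Hypothesis: "e-cigarette use will be higher, and concomitantly, combustible cigarette use will be lower, in the nicotine e-cigarette condition" than in the zero-nicotine condition.
- Test: general linear models are used "to assess the significance of the nicotine factor, using a 1-tailed alpha=0.05".
- Each outcome has its own model. For combustible use the covariates are e-cigarette use, baseline combustible use, and baseline demographic and smoking-history variables. Of the baseline variables the plan adds that "the latter will also serve as covariates in the analysis of e-cigarette use as a dependent measure".
- Error: "Thus, the 5% Type I error rate can reasonably be assigned to the 1-tailed comparison". This closes a defence of the one-tailed test, which argues that more nicotine "would only be expected to decrease use of conventional cigarettes".
- Power: for an effect size of 0.5, "a sample size of 50 per group will yield at least 80% power to detect the hypothesized effects". *Design Overview* randomises 65 per group. The documents do not explain the difference between 50 and 65.

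No section orders the two outcomes, splits alpha between them, or states what is concluded if only one is significant.

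**The concern.** With two primary tests, error and power depend on the rule that turns two p-values into one conclusion, and that rule is missing. A split result is plausible here. Smokers given nicotine pods may use more of them without smoking less, so cartridges would differ between groups and CO would not. The plan does not say whether that is a positive trial, a partly positive one or a negative one. If it were reported as positive because one primary outcome reached 0.05, the chance of a false positive would exceed the nominal 5%, and that 5% is already one-tailed. If both outcomes were needed, the power figure would not describe the claim being made.

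**Working it through.** **Inputs from the documents:** two primary outcomes; one-tailed alpha 0.05 for each; standardised effect d = 0.5; 50 per group (power statement); 65 per group (randomised).

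**Assumed, because the documents give no value:** the correlation r between the two test statistics, taken from 0 to 0.8, with both oriented so that the predicted direction is positive; the same d = 0.5 on both outcomes; unadjusted two-group comparisons.

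**1. The plan's own figure.** The noncentrality is d·√(n/2). At n = 50 it is 0.5 × √25 = 2.5. One-sided power from the noncentral t with 98 degrees of freedom is 79.9% (80.4% by the normal approximation), so the plan's 80% reproduces for one one-sided test. At n = 65 the noncentrality is 0.5 × √32.5 = 2.85, and power is 88.3%.

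**2. If either outcome suffices.** Family-wise error with both nulls true = 1 − P(Z1 < 1.645, Z2 < 1.645), where Z1 and Z2 are bivariate normal with correlation r.

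| r | Family-wise error |
|---|---|
| 0 | 1 − 0.95² = 9.75% |
| 0.5 | 8.8% |
| 0.8 | 7.5% |
| 0.9 | 6.8% |

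It reaches 5% only as r approaches 1.

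**3. If both are required.** The conclusion cannot be reached more often than either single test rejects, so error is at most 5%. Joint power is the bivariate normal probability that both tests succeed, with each margin set to the single-test power from step 1.

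| r | 50 per group | 65 per group, no loss |
|---|---|---|
| 0 | 0.799² = 64% | 0.883² = 78% |
| 0.8 | 73% | 83% |

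**4. Rules that keep family-wise error at 5%.**

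- *Fixed sequence.* The first outcome is tested at 0.05, and the second at 0.05 only if the first succeeds. Power for the first is the single-test figure: 79.9% at 50 per group, 88.3% at 65. Power to claim the second as well is the joint power in step 3.
- *Holm.* The smaller p-value is compared with 0.025 and, if that succeeds, the other with 0.05. Power for each outcome is at least that of a single one-sided test at 0.025: 80.8% at 65 per group with no loss, about 70% at 50.

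**The case against.** Four points can be made for the plan, and each limits what can be said.

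*The 5% and the 80% are correct.* They are, for one test. The error sentence defends one tail against two and makes no family-wise claim. The power sentence gives 0.5 for each main effect, so it is a per-effect statement and does not promise 80% for winning on both outcomes. A reader might infer that one of the two figures must be wrong. The documents do not support that: under a fixed sequence, 5% family-wise error and about 80% power for the first-ranked outcome hold together.

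*The hypothesis is already joint.* Its wording can be read as requiring both results. Error is then controlled, and at the 65 per group randomised the power shortfall is small or absent unless participants are lost. This is the strongest point. But the sentence is a prediction, not a success rule, and the power statement rests on 50.

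*Nothing says one significant result is enough.* True. A reader might infer that the plan permits a win on either outcome, but silence is not such a rule. The point is that silence does not exclude it either.

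*CO is in effect the lead outcome.* A reader might infer this because the one-tailed rationale mentions only conventional cigarettes. The hypothesis, however, puts e-cigarette use first and smoking reduction second. The documents do not rank the two.

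**Conclusion.** The concern holds as a missing decision rule. Two primary outcomes are each tested at one-tailed 0.05, and nothing defines or controls the error rate and power of the conclusion drawn from them together. The size depends on the rule later adopted: family-wise error of 7.5 to 9.75% if either outcome suffices; joint power of 64 to 73% (50 per group) or 78 to 83% (65 per group, no loss) if both must succeed.

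These ranges rest on an assumed correlation of 0 to 0.8, an effect of 0.5 on each outcome, and unadjusted tests. The planned models use covariates, so their actual power may differ. It does so most clearly for CO, whose model adjusts for e-cigarette use. That variable is measured after randomisation and is itself the other primary outcome, so any effect of nicotine on smoking that works through e-cigarette use would be adjusted away. The 0.5 effect and its power cannot be assumed to carry over to that test.

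**What to change.** State one rule under *Data Analysis & Statistical Considerations* that holds family-wise error at one-tailed 5% across the two primary outcomes, and restate the power for that rule and for the number expected to be evaluable. Either of two rules would do.

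- **Fixed sequence.** Name the first-ranked outcome and test it at one-tailed 0.05. Test the second at 0.05 only if the first is significant in the predicted direction; otherwise report the second with a confidence interval and no confirmatory claim. Power for the first is 79.9% at 50 per group and 88.3% at 65. The cost is that the second outcome cannot be claimed if the first fails. The ranking is the investigators' choice. If CO comes first, its primary test should not adjust for e-cigarette use; that adjusted model can be kept as a secondary analysis.
- **Holm.** No ranking is needed, and either outcome can be claimed alone. Power per outcome is at least 80.8% at 65 per group if nobody is lost, and at least about 70% at 50. The cost is somewhat lower power per outcome than a single test at 0.05.

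Either change takes a few sentences and alters no procedure or sample size. It should be made before any unblinded outcome data are seen.
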